Efficacy of Er:YAG Laser in Decontamination of Dental Implants: An In-Vitro Study

Principal Investigator:

[name], D.M.D., Ph.D.

MS Student Co-Investigator:

[name], B.D.S.

Co-Investigators:

[name].

[name], D.D.S., M.S., Ph.D.

[name].

Study Location:

Tufts University School of Dental Medicine

[name]

[name]

NCT number: NCT03100435

Protocol Version Date:

Aug 10, 2017

I. Introduction

Key Question

Is Er:YAG laser a more effective method in decontamination of titanium surfaces compared to carbon fiber curettes?

Hypothesis

Er:YAG removes biofilm more effectively from titanium surfaces than carbon fiber curettes.

Aim

The aim of this study is to compare the amount of residual biofilm on titanium discs after decontamination with Er:YAG laser and carbon fiber curette.

Background and Rationale

Dental Implants

The American Association of Oral and Maxillofacial Surgeons estimated that 69% of adults ages 35 to 44 have lost at least one permanent tooth. The advent of oral implants has revolutionized dental practice and industry as a whole.¹ Implants provide a solution for tooth loss that is predictable with long-term success.¹ A success rate of 90% has been reported for both fully or partially edentulous restorations.²⁻⁵ Different implant systems have been developed with various sizes, shapes, surfaces, and prosthetic components.⁶ The success of dental implants depends on osseointegration, a concept defined as a direct structural connection at light microscopic level between the bone and surface of the implant.⁷ The dental implant and prosthetic market in the U.S is projected to reach \$6.4 billion by 2018.

Peri-Implantitis

As well as teeth, dental implants are not immune to inflammatory lesions. The first European Workshop on Periodontology⁸ identified two disease entities surrounding implants. They have been recognized as peri-implant mucositis and peri-implantitis.⁸ Peri-implant mucositis is defined as a reversible inflammation in the soft tissues surrounding the implant, while peri-implantitis is designated as inflammation associated with loss of supporting bone around an implant.⁸ Heitz-Mayfield⁹ identified several diagnostic criteria for peri-implant diseases such as probing depth, attachment level changes, bleeding on probing, suppuration, mobility, and radiographic bone changes. The article⁹ also presented oral hygiene, history of periodontitis, diabetes, smoking, and alcohol consumption as risk factors in developing peri-implantitis. In their recent meta-analysis, Derk et al.¹⁰ estimated the prevalence of peri-implant mucositis and peri-implantitis to be 43% and 22% respectively.¹⁰ These high prevalence rates led to development of different methods for implant surface decontamination.¹¹

Treatment of Peri-Implant Diseases

Bacterial colonization on the implant surface is the main causative factor in development of peri-implant diseases.¹²⁻¹⁶ Formation of adherent bacterial biofilm on

titanium surface is critical for disease development and altering the biocompatibility of the surface.¹⁷ The literature provides evidence of peri-implantitis' microbial etiology that is very similar to advanced periodontitis, with high levels of spirochetes and non-motile anaerobic Gram-negative bacterium (*Aggregatibacter Actinomycetemcomitans*, *Porphyromonas gingivalis*, *Prevotella intermedia*, *Tannerella forsythia*, *Treponema denticola*).¹⁸ Furthermore, the presence of multiple components in a single dental implant, i.e. fixture, abutment, and crown, accumulate more plaque than natural dentition.^{19, 20} A study by Pontoriero et al.²¹ demonstrated a cause and effect relationship between plaque accumulation and peri-implant mucositis. Surface debridement constitutes the basis of treatment of peri-implant disease.¹⁷ However, complete debridement is not a simple task.

Mechanical hand instrumentation using curettes to remove biofilm and calculus is still the basis for any periodontal therapy. Based on the extensive evidence supporting hand instrumentation in treatment of periodontitis, hand instruments were proposed for the treatment of peri-implant diseases. Scalers of different materials were made specifically for implant surfaces. These scalers were made with similar or lower external hardness, in order not to produce scratches on the implant surface and not to make the implant surface more plaque retentive. Furthermore, a damaged surface impairs adhesion of fibroblasts and lowers biocompatibility of the implant.^{22, 23} Fox et al.²³ studied the effect of stainless steel, titanium, and plastic curettes on implant surface roughness by scanning electron microscopy (SEM). Surprisingly, the roughest surface was produced by the titanium curettes followed by stainless steel and plastic. The plastic surface alteration was determined to be insignificant. Homiak et al.²⁴ in their SEM study on implant abutments confirmed that stainless steel instrument produced a rougher surface. Whereas, plastic scalers rounded off sharp edges and smoothed the surface but changes were not extremely dramatic. Carbon fiber curettes are another alternative to plastic curettes, which do not significantly damage the implant surface.²⁵ Strooker et al.²⁶ reported decrease in Gingival Index and number of bacterial colonies in patients treated by mechanical instrumentation using carbon fiber curettes.

Karring et al. showed that mechanical non-surgical therapy alone is not sufficient to treat peri-implantitis.²⁷ Persson et al.²⁸ compared using curettes with ultrasonic devices, and reported failure of both measures to resolve the disease. Renvert et al. observed mechanical non-surgical therapy could only be effective in peri-implant mucositis cases only, and results could be enhanced by the adjunctive use of antimicrobial rinses.¹⁷ No treatment protocols have received full consensus as a standard of care, as most treatments were unable to achieve complete inflammation resolution or surface decontamination.^{17, 29, 30} Therefore, different modalities of treatment have been developed to overcome inadequacies such as sustained antibiotics release, antiseptics, air abrasion, and laser therapy.¹⁷

Er:YAG Laser

Laser therapy has been advocated for implant surface decontamination.^{31, 32} Several types of lasers have been evaluated for this purpose such as erbium-doped yttrium-aluminum-garnet (Er: YAG), carbon dioxide (CO₂), gallium-aluminum- arsenide

(GaAlAs) diode, neodymium-doped yttrium–aluminum–garnet (Nd:YAG) and erbium- and chromium-doped yttrium–scandium–gallium–garnet.^{31, 32} CO₂, diode, and Er:YAG lasers have been implicated for irradiation of implant surfaces because they are poorly absorbed by the implant and do not raise surface temperature.³³ The Er:YAG laser appears optimal for implant decontamination as the Er:YAG laser energy is primarily absorbed by water, resulting in vaporization of bacteria and minimal surface alterations on the implant surface.^{34, 35}

Several investigations have been carried out on the effectiveness of Er: YAG laser in surface decontamination. Kreisler et al.³⁶ incubated *Streptococcus sanguinis* over titanium discs and irradiate them with power 60 and 120 mJ/pulse at 10 Hz. Their results reported reduction ranges from 98.3% to 99.94%. Matsuyama et al.³⁷ evaluated Er: YAG in six contaminated healing abutments. They showed that Er: YAG at 30 mJ/pulse and 30 Hz with water spray was capable of effectively removing plaque and calculus on the implant abutments without injuring their surfaces. Quaranta et al.³⁸ explored different types of implant surfaces contaminated with *Porphyromonas gingivalis*. They observed values of 76.2% for machine tested implants, 90.9% for titanium plasma spray implants, and 98.3% for sandblasted and etched implants. A minimal residual bacterial presence was observed in all groups. Sennhenn-Kirchner et al.³⁹ evaluated efficacy against *Candida albicans* incubation. They found Er:YAG laser damaged the fungal cells to a great extent wherever it was applied on direct contact. Decontamination efficacy was dose-dependent with values ranging from 59% following irradiation with 80 mJ/pulse at 5 Hz⁴⁰ to 99.94% following irradiation with 120 mJ/pulse at 10 Hz.³⁶ Schwarz et al.⁴¹ in a canine study showed Er:YAG to be more suitable to promote re-osseointegration than ultrasonics or plastic curettes.

Studies evaluated efficiency of decontamination using scanning light microscopy, scanning electron microscopy (SEM), counting the colony forming units (CFU), bacterial smears, and photometric XTT–formazan evaluations.³¹ Molecular Probes' LIVE/DEAD® BacLight™ Bacterial Viability Kits provide a novel two-color fluorescence assay of bacterial viability that has proven useful for a diverse array of bacterial genera. LIVE/DEAD BacLight allow researchers to easily, reliably and quantitatively distinguish live and dead bacteria in minutes, even in a mixed population containing a range of bacterial types.

Since no consensus treatment for peri-implantitis has yet emerged, there is an urgent need for quantitative evaluation of the available treatment options. This study is designed to compare the biofilm removal efficiency of the Er:YAG laser with mechanical biofilm removal tools. Our goal is to establish whether Er:YAG laser significantly improves titanium surface decontamination. Our findings may contribute to the development of novel and efficient treatment of peri-implantitis.

Standard of Care in the TUSDM Periodontal Clinic

For patients who are experiencing a failing dental implant, the treatment starts with improving overall oral hygiene and controlling any etiological factors that prevent restoration of optimum oral health. The second step usually involves a surgical

intervention method such as open flap debridement, followed by implant decontamination using Er:YAG, titanium brushes, or plastic curettes. If the bony defect developed by the disease process is contained, bone regenerative therapy may be used.

I) Research Plan

A) Experimental Design

This study is designed to investigate the efficiency of biofilm decontamination of Er:YAG laser compared to carbon fiber curette. The first phase is clinical wherein experimental subjects will be recruited. Full periodontal examination will be performed and alginate impressions will be taken. A custom mouth guard that holds multiple titanium discs will be fabricated. Experimental subjects will be instructed to wear this mouth guard for 72 hours, during which time a natural bacterial biofilm will form on the disc surfaces. The second phase of the study will be performed after collecting the discs from the subjects and exposing them *ex vivo* to one of four treatment groups 1) Er:YAG laser, 2) carbon fiber curette, 3) titanium brush, and 4) no treatment (control). The biofilm will be stained with LIVE/DEAD *BacLight* dye and the residual biofilm will be visualized under fluorescence microscopy. Quantification of residual biofilm will be performed using image analysis software (Image J, NIH). Statistical methods will be used to determine the significance of each treatment modality. The primary outcome of the study is the percent area of the titanium disc covered by biofilm.

B) Power Calculation

A power calculation was performed via the statistical software nQuery Advisor (Version 7.0). Using the results of Schwarz et al.⁴² for anticipated means and standard deviations, and assuming that the mean for the combination group is equal to the mean of the Er:YAG laser group, a sample of 8 subjects, allowing for ~20% dropout with a final projected sample size of 6 (8 discs per subject, 64 total discs) is sufficient for a Type I error rate of 5% and a power over 99%. Discs retrieved from each mouth guard will be randomized over the 4 treatment groups using the "sample" function of the statistical software package R (Version 3.1.2), so that each subject will contribute two discs to each treatment group.

C) Statistical analysis

Descriptive statistics (means, standard deviations, medians, and inter-quartile ranges) will be computed by group. Statistical significance will be assessed via repeated-measures ANOVA if the data are normally distributed, and Friedman's test if the data are not normally distributed. $P < 0.05$ will be considered statistically significant. The analysis will be conducted using SPSS Version 22.

D) Products

Titanium discs will be supplied by Straumann USA (Andover, MA).

E) Subject Characteristics

Inclusion criteria:

- Adults (18 years or older).
- Presence of enough teeth to support the mouth guard.
- English proficiency.
- Subjects diagnosed with clinical health, gingivitis, or slight chronic periodontitis defined as periodontal inflammation with slight (1-2mm) attachment loss. Subjects will not be stratified based on oral health.

Exclusion criteria:

- Subjects with insufficient dental support for the mouth guard
- Subjects diagnosed with moderate or severe chronic periodontitis.
- Subjects with known allergy to acrylic or titanium.
- Subjects who smoke cigarettes, cigars, snuff tobacco, or any other form of smoking.
- Subjects with a history of antibiotic treatment within the last six months.
- Subjects with contraindications to wearing a mouth guard, such as chronic obstructive pulmonary disease or severe sleep apnea.
- Subjects with uncontrolled or debilitating medical conditions, including but not limited to subjects with uncontrolled diabetes, hematologic disorders, cancers, immunosuppression, severe cardiovascular disease, or uncontrolled thyroid disease
- Subjects that are currently pregnant according to self-report as hormonal changes may affect the outcomes of the study.
- Subjects who are unable or unwilling to sign the informed consent form (ICF).
- Subjects may not participate in this study if they concurrently participate in another research study.

Subject withdrawal and termination criteria:

- Subject may withdraw from the study at any time. Subjects may remain patients of TUSDM if they decide to withdraw from the study.
- Investigators may terminate subjects if they no longer fulfill inclusion criteria, if an exclusion criterion is met, or if they do not show up for scheduled study visits. Subjects may remain patients of TUSDM if they are withdrawn from the study. If a subject withdraws from the study early and returns the mouth guard, the mouth guard and the titanium discs will not be analyzed and will be disposed of. Subjects withdrawing from the study early will not be eligible for the \$25 gift card.
- Unanticipated Adverse Device Event

The Principal Investigator will determine whether subjects (either withdrawn subjects or subjects completing the study) are in need of additional treatment and/or follow-up observation. Potential unforeseen adverse events may include allergic reaction to acrylic or titanium, or irritation of the gum by the mouth guard.

Subjects and/or their insurance will be responsible for the cost of any standard of care follow-up visits or additional treatment that is not part of this study.

F) Assessment

1) Risk

Risks associated with standard of care periodontal examination for periodontal patients include sensitivity, discomfort, pain and bleeding during examination. Swelling is not expected.

Risks associated with the mouth guard include speech alteration and esthetic concerns. Abstaining from the use of toothpaste and mouthwash for 3 days poses minimal health risk as the principal factor in oral hygiene is the mechanical plaque removal by the toothbrush bristles. The risk associated with brushing without toothpaste or not using mouthwash for 3 days is halithosis (bad breath). Also, disc de-attachment presents another risk of swallowing or aspirating. That risk will be minimized by close adaptation of the mouth guard to the disc and the use of adhesive (PeriAcryl).

Potential unforeseen adverse events may include allergic reaction to acrylic or titanium, or irritation of the gum by the occlusal mouth guard.

Loss of confidentiality is also a risk of participation. This risk will be minimized by following the procedures outlined in the confidentiality section.

2) Benefits

There are no specific benefits to study participants in this study. Potential benefits to society might include improved treatment protocols for peri-implantitis. Potential benefits to science might include increased understanding of methods used to decontaminate implant surfaces.

3) Alternatives

The alternative is to not participate in the study and receive standard of care periodontal treatment at the TUSDM clinic at standard clinic costs.

G) Study Procedures

Visit 1: Screening and consent (Approximately 90 minutes)

Subjects will be asked to read the informed consent form (ICF). Subjects will be given ample time to have any questions answered. If a subject decides to participate, he or she will be asked to sign the ICF. A copy of the ICF will be given to the subject.

Medical history and demographic information will be collected. To determine eligibility periodontal examination will be performed according to standard of care, including

measuring pocket depth, recession, attachment level, and bleeding on probing. If full periodontal examination was performed at TUSDM no more than 6 months ago, then existing records may be used to determine eligibility. As periodontal measurements are not a primary outcome, existing periodontal measurements collected by other TUSDM dentists may be used.

Inclusion and exclusion criteria will be considered and eligibility for the study will be determined.

Alginate impression for the maxillary teeth will be taken using stock plastic trays according to subject's arch size in conformance with standard of care practice.

After Visit 1 (In the Laboratory): Impression pouring, cast, and mouth guard fabrication

After the visit, alginate impressions will be disinfected and poured in the dental laboratory using dental stone. Subjects are not required to stay for the length of time of laboratory procedures. Dental stone will be allowed to set for 45 minutes before cast retrieval. After retrieval, casts will be trimmed according to laboratory standards. Titanium discs (5mm diameter, 1 mm thick, 4 discs each on the left and right premolar/molar areas, a total of 8 discs per subject, supplied by Straumann USA) will be fixed on the buccal surfaces of posterior teeth of the casts. A computerized positive pressure thermal-molding machine (Biostar, Great Lakes Orthodontics, Tonawanda, NY) will be used to fabricate a 1mm thick mouth guard on top of the cast, covering the attached titanium discs. The mouth guard will be removed from cast and trimmed to proper size. New titanium discs of the same size and count will be secured in mouth guard compartments with surgical adhesive (PeriAcryl, Salvin Dental Specialties, Charlotte, NC, Figure 1). The final shape of the appliance will resemble an occlusal mouth guard. The mouth guard will be disinfected in 0.12% chlorhexidine.

Figure 1: Gosau et al.⁴³

Visit 2: Within 2 months of Visit 1- Mouth guard delivery (approximately 60 minutes)

Medical history will be reviewed. Eligibility criteria will be re-evaluated. The mouth guard will be inserted into subject's mouth and adjusted for complete fitting and comfort. Intra-oral photograph will be taken in frontal view of the subject's teeth and gums while wearing the mouth guard.

Subject will be asked to use the mouth guard for 72 hours continuously except during eating. Patient will be instructed to brush their teeth twice daily without the use of toothpaste and to floss once daily. Mouth rinses will be prohibited. These instructions will be given verbally with demonstration facing a mirror. The same instructions will be provided to study subjects in writing as well.

Visit 3: 3 days after Visit 2- Mouth guard retrieval (approximately 30 minutes)

Medical history will be reviewed. Eligibility criteria will be evaluated. Mouth guard will be retrieved from patient and stored until analysis.

After Visit 3(In the laboratory): Group Assigning, Experimental Treatments, and Measurements

After the visit, titanium discs will be separated from the mouth guard. Subjects are not required to stay for the length of time of laboratory procedures. Care will be taken not to disturb the surface biofilm. The back side of each disc will be numbered 1-64 and the subject and intraoral location will be recorded. Discs retrieved from each occlusal mouth guard will be randomized over the 4 treatment groups using the "sample" function of the statistical software package R (Version 3.1.2), so that each subject will contribute two discs to each treatment group.

After treatment, discs will be placed individually in a 24-well tissue culture plate, rinsed with saline and stained using the LIVE/DEAD BacLight dye Kit (Thermo Fisher Scientific, Waltham, MA). Equal volumes of Component A and Component B will be combined in a microfuge tube. The dye mixture will be added to the discs and incubated at room temperature in the dark for 15 minutes. The discs will be observed in a fluorescence microscope equipped with FITC/TRITC filter sets (Zeiss Axiovert 200, Carl Zeiss AG, Oberkochen, Germany). Percent biofilm covered area will be calculated with digital image analysis software (ImageJ, NIH).

Appointment Procedures	Visit 1 Screening/ Baseline	Visit 2 Baseline (Treatment Day 0)	Visit 3 Retrieval (Treatment Day 3)
Consent Form	X		
Demographics	X		
Medical/Dental History	X	X	X
Inclusion/Exclusion Criteria	X	X	X
Oral Examination	X		
Digital Photography		X	
Alginate Impressions	X		
Compensation			X

Mouth guard Delivery		X	
Mouth guard Instructions		X	
Mouth guard Retrieval			X

H) Subject Safety

1) Adverse Event Reporting

Adverse Events

An adverse event is any untoward or unfavorable medical occurrence in a human subject, including any abnormal physical exam or laboratory finding, symptom, or disease, temporally associated with a subject's participation in the research. An adverse event in this study may be the loss of the mouth guard or the loss of a titanium disc.

Adverse events will be recorded in source documents and on case report forms. All adverse events and non-serious situations will be recorded, monitored, and reported to the IRB at time of continuing review or at the study's termination if this occurs before the study's next continuing review.

Adverse events will be recorded in source documents and on case report forms. All adverse events and non-serious situations will be recorded, monitored, and reported to the IRB at time of continuing review.

Serious Adverse Events

A serious adverse event is one that results in death, or is life-threatening, or results in hospitalization or prolongation of existing hospitalization, or results in a persistent or significant disability/incapacitation, or results in a congenital anomaly/birth defect, or may jeopardize the subject's health and may require medical or surgical intervention to prevent one of the other outcomes listed above. Based on clinical experience with mouth guards it is unlikely that study subjects will experience any serious adverse event. Should a serious adverse events occur, will be recorded in source documents and on case report forms. Serious Adverse Events that meet the criteria of an unanticipated problem will be reported to the IRB within 5 business days following the Reportable New Information Policy. Serious adverse events that do not meet the criteria for an unanticipated problem will be recorded in source documents and on case report forms, and included in the summary reporting form at the continuing review or at the study's termination if this occurs before the study's next continuing review.

Unanticipated Problems

An unanticipated problem is an incident, experience, or outcome that meets all of the following criteria: 1) The nature, severity, or frequency is unexpected for the subject population or research activities as described in the current IRB approved protocol, supporting documents, and the ICF(s); 2) it is related or possibly related to

participation in the research; 3) it suggests the research may place the subject or others at a greater risk of harm than was previously recognized.

Unanticipated problems will be recorded in source documents and on case report forms. Unanticipated problems will be reported to the IRB within 5 business days after the PI/study team becomes aware of the problem. A Reportable New Information Form will be submitted to the IRB no later than 5 business days after the PI/study team becomes aware of the problem.

Subject Participation

2) Screening

[name] will conduct screening as outlined in Visit 1.

3) Informed Consent

[name] will introduce the study.

Written consent will be obtained following "SOP: Written Documentation of Consent (HRP-091)." Consenting will take place in a private clinic bay area and the patient will be given as much time as he/she needs to consider participation. The participant will be invited to include or exclude any associates (e.g., loved ones) in the consent process.

Patients will be asked to read the consent form and given ample opportunity to have their questions answered. To avoid coercion, the consenting investigator will read through the copy of the consent form with the participant section by section, making sure the participant understands each section and has an opportunity to ask questions. If at any time the participant indicates s/he is not interested in participation, the meeting will end.

If after going through the consent form, the participant indicates s/he would like to discuss the study with associates or think about participating, then the meeting will be ended and the participant will be asked to contact the study when s/he makes her decision. If the participant contacts the study in the future for participation, s/he will be invited back to the clinic, and if informed consent is given at that time, study activities will begin then.

If the participant indicates s/he may be interested in participating after going through the consent form with the investigator, and the investigator determines the participant has the capacity to provide informed consent, the participant will be asked to provide informed consent at that time. Patients will certify their willingness to participate in the study by signing and dating the IRB approved informed consent document. The subject will be given a copy of the consent form.

If any new finding requires any change to the informed consent form, the subject will be re-consented.

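### Does Friedman's test misfit this design because each subject gives two discs per treatment and no rule for combining them is stated?

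*Combined protocol and SAP*

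**What the plan says.** Under I) Research Plan, A) Experimental Design, four treatments are compared and the outcome is defined for the disc: "The primary outcome of the study is the percent area of the titanium disc covered by biofilm". B) Power Calculation plans 8 enrolled subjects with a "final projected sample size of 6 (8 discs per subject, 64 total discs"), and adds that "each subject will contribute two discs to each treatment group". G) Study Procedures (After Visit 3) repeats that allocation and states "The back side of each disc will be numbered 1-64 and the subject and intraoral location will be recorded".

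C) Statistical analysis is one short paragraph. It gives "Descriptive statistics (means, standard deviations, medians, and inter-quartile ranges) will be computed by group", then "Statistical significance will be assessed via repeated-measures ANOVA if the data are normally distributed", and "Friedman's test if the data are not normally distributed". It does not say whether the two discs in a subject-by-treatment cell are averaged, kept as replicates or handled in some other way. H) Subject Safety, 1) Adverse Event Reporting allows for lost material: "An adverse event in this study may be the loss of the mouth guard or the loss of a titanium disc".

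**The concern.** Friedman's test ranks one value per treatment within each block. Here a subject supplies two values per treatment, so the test cannot be run on the raw disc file without a prior step, and none is written. The fallback could well be needed: the outcome is a bounded percentage, and the background section cites laser reductions of up to 99.94%, so laser discs may sit close to zero while controls do not.

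The disc-level outcome and the 1 to 64 numbering could also invite a disc-level data file. If each subject's discs were entered as two separate blocks, discs from one mouth would count as independent evidence. That could raise the type I error. The Friedman result would also depend on which laser disc happened to share a row with which curette disc. The reported standard deviations would differ too, according to whether they were taken over discs or over subject means.

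**Working it through.** **Counts stated in the plan.** 6 / (1 − 0.20) = 7.5, rounded up to 8 subjects; 8 × 8 = 64 discs; 8 discs / 4 treatments = 2 per cell. These agree with the plan. One value per cell gives 6 × 4 = 24 values at the projected size, or 8 × 4 = 32 if every subject completes. The power of over 99% cannot be reproduced because the means and SDs behind it are not printed, but the present question does not depend on it.

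**Friedman's test: how many sensible reductions are there?** For two values a and b, the mean is (a + b)/2, the median is (a + b)/2, and the sum is a + b, twice the mean. All three order the treatments identically within a subject, so they give the same ranks and the same test statistic.

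**ANOVA: averaging against a replicate factor, complete data.** Let m(i,j) be the mean of the two discs for subject i on treatment j, with n subjects.
- Treatment sum of squares, replicate-factor analysis: 2n × Σ (treatment mean − grand mean)². On averaged values: n × the same sum.
- Subject-by-treatment sum of squares, replicate-factor analysis: 2 × Σ (m(i,j) − subject mean − treatment mean + grand mean)². On averaged values: 1 × the same sum.
- The factor 2 cancels in F. The degrees of freedom are 3 and 3(n − 1) either way: 3 and 15 at n = 6, 3 and 21 at n = 8.

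A numerical check agreed in 20 of 20 simulated datasets at each n (difference below 1e-14).

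**The harmful alternative: discs entered as 2n separate blocks.** The plan does not describe this. Assume a within-subject variance of 1, of which a share s is subject-by-treatment variation common to the two discs of a cell, and 1 − s is disc variation. The documents give no value for s.
- Expected treatment mean square under the null: 2s + (1 − s) = 1 + s.
- Expected error mean square at n = 6: [15(1 + s) + 18(1 − s)] / 33 = 1 − s/11.
- Ratio: 1.00 at s = 0; 1.1/0.991 = 1.11 at s = 0.1; 1.2/0.982 = 1.22 at s = 0.2; 1.5/0.955 = 1.57 at s = 0.5.

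The F statistic is therefore inflated only when s is above 0. Simulated type I error at a nominal 5% (40,000 null datasets per setting; chi-square critical value for Friedman's test):

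| Assumed s | ANOVA, 2n blocks, n=6 | Friedman, 2n blocks, n=6 | ANOVA, 2n blocks, n=8 | Friedman, 2n blocks, n=8 |
|---|---|---|---|---|
| 0 | 5.0% | 4.4% | 5.1% | 4.6% |
| 10% | 6.9% | 5.8% | 7.0% | 6.1% |
| 20% | 8.8% | 7.4% | 8.9% | 7.3% |
| 50% | 16.5% | 12.7% | 16.2% | 12.6% |

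On averaged discs the error is 4.9 to 5.1% (ANOVA) and 3.6 to 4.3% (Friedman) over the same settings.

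**Dependence on pairing, again only if discs are entered as 2n blocks.** An analyst uses one pairing, so the relevant figure is how often two randomly chosen pairings disagree at the 5% level. Under the null this is 4.2 to 6.4% of datasets at n = 6 and 4.0 to 6.7% at n = 8. At an effect giving 99% power on averaged values (one assumed pattern of means) it is 0.4 to 3.1%. Asking whether any of 1,000 pairings flips the result gives 26 to 36% under the null, but that count grows with the number of pairings tried and is not the chance that a reported result is arbitrary. Averaging removes the dependence on pairing.

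**The case for a change.** The strongest case for a change is that pre-specification exists to settle such choices before results are seen. Section C is the whole analysis plan, one sentence would settle this one, and the wrong choice could more than triple the type I error (16.5% against 5% at an assumed share of 50%). It is true that the step is not written and that the outcome and numbering are at disc level.

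The wrong choice, however, requires an analyst to set aside a sample size stated in subjects, two tests chosen because treatments are compared within subjects, and a procedure that records the subject for every disc. Numbering discs singly is needed for randomisation and for masked or orderly handling of specimens; it does not define the unit of analysis.

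Two smaller points stand in part. If a disc is lost, averaging and the replicate-factor ANOVA no longer coincide exactly. The remaining disc can still represent its cell, and only the loss of both discs of a cell leaves a gap in that subject's block. The documents give no rate for this, and E) Subject Characteristics already leaves out all discs from subjects who withdraw early. SDs over discs and over subject means are different quantities, but these are descriptive figures whose basis can be labelled when reported. With complete data the group means are the same either way.

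**Conclusion.** This is a gap in detail that an analyst following the plan fills sensibly, so no change is called for. Read as written, the design leads to one value per subject and treatment. The mean, median and sum of two discs give the same Friedman test, the two natural forms of the ANOVA give the same F with complete data, and the type I error on averaged values stays at or below about 5%.

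The possible harm depends on discs being treated as separate subjects, which the plan does not propose. For type I error it also depends on a subject-by-treatment variance above zero. Under assumed shares of 10 to 50% the error would then be about 6 to 17%; at a share of 0 it is 4.4 to 5.1%. That the step is unwritten is certain. The size of any harm rests on assumed variance shares, because the documents give none.
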